Hyperglycemic clamp: The RISE protocol was used to calculate first-phase C-peptide response as the mean incremental response above baseline over minutes 2-10, and the maximal C-peptide response as the mean incremental response during minutes 184-190 above the mean at min 170-180. Insulin sensitivity was calculated as described for the hyperglycemic clamp.

Statistics:

a. *Analyses*. The primary analysis for each aim will be a mixed model, using all available data and utilizing the estimated correlation between measurement times. The mixed model is less biased towards statistically significant results in the context of missing data, and/or when a moderate to high correlation exists between outcome measures. For Aim 1, the primary outcome will be pancreas lipid. Statistical models will include time, diet, and the time-by-diet interaction. Other potential covariates (e.g., gender, race, total body fat, adherence to diet) will be explored in preliminary analyses. Similar analyses will be conducted for hepatic lipid and visceral adipose tissue. For Aim 2, the primary outcome will be beta-cell function, as reflected in first phase C-peptide secretion from the hyperglycemic clamp. Statistical models will include time, diet, and the time-by-diet interaction. Other potential covariates (e.g., gender, race, total body fat, adherence to diet, insulin sensitivity) will be explored in preliminary analyses. Similar analyses will be conducted for PhiD from the MMTT, and insulin sensitivity from the hyperglycemic clamp. Food records will be coded to assess adherence as a dichotomous variable, and adherence

will be defined as +/- 10 percentage points of the targeted carbohydrate intake. For Aim 3, the primary variable of interest is the race-by-diet interaction term, which will be added to the models from Aims 1 and 2. If either of these interaction terms is significant, the data will be analyzed separately within each race group. Influential data points and outliers will be examined in a sensitivity analyses.

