Correlative analyses will be conducted between changes (week 12 minus baseline) in measures of glucose metabolism (e.g., glucose AUC from liquid meal test, HbA1c), markers of inflammation, visceral fat, and hepatic/pancreatic lipid with Pearson's correlations coefficients (adjusting for relevant confounding variables). The correlation between change in pancreas lipid and change in first-phase C-peptide secretion will be examined, adjusting for insulin sensitivity. For all analyses, variables known to deviate from a normal distribution will be log transformed.

All statistical tests will be two-sided and will be performed using an alpha level of 0.05.

Statistical analyses will be performed using SAS Version 9.4®. Baseline descriptive characteristics will summarized as means (SD) or proportions to include demographic, clinical, and other measures.

b. Power calculation. Based on our published data, a sample size of 15 in each group will have 80% power to detect a difference in means of -89.700 (the difference between a Group 1 mean, μ_1 , of 6.400 and a Group 2 mean, μ_2 , of 96.100) in first-phase response at week 12 assuming that the common standard deviation is 84.639 using a two group t-test with a 0.050 two-sided significance level. Because we believe that the association between pancreas lipid and beta-cell function will be stronger in African-Americans, we have elected to target a final sample size of

15 participants per diet-race group (total of 60 participants with complete data). Using the Fisher r-to-z transformation, a value of z can be calculated that can be applied to assess the significance of the difference between two correlation coefficients, r_a and r_b , found in two independent samples. Given 30 subjects in each race group, we will be able to detect a difference of 0.3 with a one-sided alpha of 0.05. We will recruit 80 participants (20 per diet-race group) to account for missing data, potential drop-outs, or for participants who have to withdraw from the study due to problems with glycemic control.

c. Randomization

The study statistician ([name]) will prepare a closed envelope randomization for the two treatment arms stratified by race group using Proc Plan in SAS Ver. 9.4®. Patients will receive their group assignment following baseline testing.

Patient management following the study:

[figure not shown]

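### Aim 3's primary term is named as race-by-diet, neither crossed with time nor adjusted for baseline; read literally, it pools the pre-diet visit with week 12

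*Combined protocol and SAP*

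**What the plan says.** Under Statistics, a. Analyses, every aim uses a mixed model "using all available data and utilizing the estimated correlation between measurement times". The Procedures section places the OGTT and clamp at baseline and after 12 weeks. For Aims 1 and 2, "Statistical models will include time, diet, and the time-by-diet interaction". Race appears there only in a list of covariates that might be considered.

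For Aim 3, "the primary variable of interest is the race-by-diet interaction term, which will be added to the models from Aims 1 and 2". The result also decides what follows: "If either of these interaction terms is significant, the data will be analyzed separately within each race group".

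Section c specifies "randomization for the two treatment arms stratified by race group", and adds: "Patients will receive their group assignment following baseline testing". Section b gives power for a two-group comparison "in first-phase response at week 12 assuming that the common standard deviation is 84.639", with 15 completers per diet-race cell as the target. Its only race-related power statement concerns a difference between correlations; none is given for race-by-diet.

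**The concern.** In a model with two visits, one before the diet starts and one after, the diet effect is the time-by-diet term. The question whether race modifies that effect is therefore answered by race-by-diet-by-time, or by race-by-diet at week 12 with baseline taken into account. A two-way race-by-diet term that is not crossed with time describes a race difference in the diet contrast pooled over both visits. Half of those data were collected before anyone had been assigned a diet.

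Two things are at stake. This is the primary test of Aim 3, and it is the gate for analysing the races separately. A reader of a reported race-by-diet result also could not tell whether it concerns the response to diet or a level that includes pre-diet data. The diet tests of Aims 1 and 2 are not affected.

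**Working it through.** **Inputs from the plan.** SD 84.639, difference 89.7, two-sided 0.05, 15 per group (section b); 15 per diet-race cell, 60 in all.

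**Assumptions.** A week-12 interaction D of 89.7, meaning the plan's whole diet difference in one race and none in the other, and a baseline-to-week-12 correlation ρ from 0 to 0.7. The plan gives neither.

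**The plan's own figure.** Two-group t-test, 15 per group: noncentrality 89.7 / (84.639 × √(2/15)) = 2.90 on 28 df, giving 80.0% power. The stated 80% reproduces.

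**What the literal term estimates.** Let k be the week-12 SD divided by the baseline SD. With a race main effect in the model and complete data, the generalized least squares estimate is

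w × (week-12 contrast) + (1 − w) × (baseline contrast), with w = (1 − ρk) / (1 + k² − 2ρk).

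- With equal SDs (k = 1), w = 0.50 at any ρ. Diet is assigned within race after baseline testing, so the expected baseline contrast is zero and the target is D/2 = 44.85.
- With unequal SDs and an unstructured covariance, w varies. At ρ = 0.5 it is 0.71 / 0.29 / 0.14 for k = 0.8 / 1.25 / 1.5. For k from 0.8 to 1.5 and ρ from 0.3 to 0.7 it runs from 0.85 down to −0.04.

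**Power with equal SDs.** The SE of a one-visit interaction contrast is 84.639 × √(4/15) = 43.71. Then:

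- As written: effect D/2, SE 43.71 × √((1 + ρ)/2), 56 df.
- Race-by-diet-by-time: effect D, SE 43.71 × √(2(1 − ρ)), 56 df.
- Week 12 adjusted for baseline: effect D, SE 43.71 × √(1 − ρ²), 55 df.

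At ρ = 0.5 the noncentralities are 44.85/37.85 = 1.185, 89.7/43.71 = 2.052 and 89.7/37.85 = 2.370.

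| Power at D = 89.7 | ρ = 0 | 0.3 | 0.5 | 0.7 |
|---|---|---|---|---|
| As written | 30% | 24% | 21% | 19% |
| Race-by-diet-by-time | 30% | 40% | 52% | 74% |
| Baseline-adjusted | 52% | 56% | 64% | 81% |

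| D detectable with 80% power | ρ = 0 | 0.3 | 0.5 | 0.7 |
|---|---|---|---|---|
| As written | 176 | 201 | 216 | 230 |
| Race-by-diet-by-time | 176 | 147 | 125 | 97 |
| Baseline-adjusted | 125 | 119 | 108 | 89 |

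With half the interaction (44.85), power over the same correlations is about 9 to 11% as written, 11 to 26% three-way and 17 to 29% baseline-adjusted.

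**Simulation check.** 4,000 trials per setting, unstructured covariance, ρ = 0 / 0.3 / 0.5 / 0.7. As-written type I error was 5.2 / 5.8 / 5.8 / 5.0%. At D = 89.7 its mean estimate was 44.3 / 44.5 / 44.6 / 45.2 and its power 31 / 24 / 23 / 21%.

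**Chance baseline imbalance.** A one-SE imbalance (43.71) shifts the as-written estimate by 43.71 × (1 + ρ)/2, which is 28 / 33 / 37 at ρ = 0.3 / 0.5 / 0.7, against a target of 44.85. Power is then about 53 to 55% if the imbalance favours the effect and about 1% or less if it opposes it. The three-way estimate shifts by 43.71 × (ρ − 1) = −31 / −22 / −13 against 89.7. The baseline-adjusted estimate does not shift.

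**If race is not a main effect.** Suppose race-by-diet is added to the listed terms alone and the races differ by a constant amount with no modification of the diet effect. In simulation (ρ = 0.5, equal SDs, 1,500 runs), race differences of 0.25 / 0.5 / 0.8 SD gave rejection in 13 / 33 / 68% of trials with product coding and 15 / 49 / 89% with class coding on 2 df.

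**The case against.** The strongest reply is that race-by-diet is shorthand. Since the diet effect in the Aim 1 and 2 models is time-by-diet, adding race-by-diet to those models can be read as letting race modify that effect. The plan thinks in changes elsewhere: "Correlative analyses will be conducted between changes (week 12 minus baseline) in measures of glucose metabolism", and Supplementary Table 1 tabulates change by race and diet. This reading is reasonable and cannot be ruled out. It does not remove the point, because no section writes the term out and the literal wording gives a different test.

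The size also rests on assumed inputs. With a smaller interaction all three tests have low power, and much of the shortfall is sample size, which no choice of term repairs. At correlation 0 the literal term loses nothing against the three-way term. The plan log-transforms variables that depart from normality, so 84.639 may not be on the analysis scale. The loss of nearly all power applies only to an adverse imbalance; the average over randomizations is the 19 to 30% in the table. All of this stands.

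A reader might go further and infer that the test is invalid, or that a reported Aim 3 result was diluted. The documents support neither. With race in the model, randomization within race after baseline keeps type I error at about 5% on average, and nothing shows which term was fitted. Supplementary Table 1 does not show dilution either: it covers insulin sensitivity, gives no cell sizes, and its change column does not match the differences between its visit means.

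**Conclusion.** The point holds as one of specification. Time and time-by-diet are in the models, but the Aim 3 term is not crossed with time, baseline is not a covariate, and a race main effect is not fixed. Followed to the letter with race included, the test mixes pre-diet data into its estimate. One half is the weight only under equal variances and complete data.

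Under the stated assumptions the literal term has less power than a baseline-adjusted test at every correlation examined, and less than the three-way term at every positive one. At correlation 0.5 the figures are 21% against 64% and 52%. If the race main effect is left out, control of type I error is lost as well. Confidence is high that the wording is inexplicit and that its literal reading pools the visits. Whether any power was actually lost cannot be told from the documents. The Aim 1 outcome, pancreas lipid, cannot be quantified because the plan gives no SD for it. It should be fixed, because this is a primary test and the correction is cheap.

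**What to change.** Define the Aim 3 test in one of two ways:

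- race-by-diet-by-time, with race and all lower-order race terms in the model. This stays closest to the existing models, though chance baseline imbalance still shifts the estimate; or
- with more power, the week-12 race-by-diet contrast adjusted for baseline, with race as a main effect. The equivalent contrast from a mixed model with a common baseline mean within race would also serve and keeps all available data.

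Name the covariance structure. Report the diet effect in each race with a confidence interval, as contrasts from that one model and whether or not the interaction is significant.

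Week-12 results already exist, so state which term was fitted. If the literal term was used, refit once and disclose the refit as made after results were known. The cost is one sentence in the plan and at most one refit labelled post hoc, with no new data or participants. Disclosure does not fully remove the weakness of changing a test after results are known, so the result of the fitted term should be shown beside the refit.

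### The claim that 30 per race group can detect a correlation difference of 0.3 gives no power and no correlations, holds at 80% power only when both correlations are strong, and uses a one-sided alpha against the plan's two-sided rule

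*Combined protocol and SAP*

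**What the plan says.** Section b (Power calculation) makes two power statements. The first is a two-group t-test on first-phase response, for which "a sample size of 15 in each group will have 80% power"; means, standard deviation and a two-sided 0.05 level are all given.

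The second concerns race. The target of 15 completers per diet-race group, 60 in all, is introduced with the reason "Because we believe that the association between pancreas lipid and beta-cell function will be stronger in African-Americans". The plan then names the Fisher r-to-z method to "assess the significance of the difference between two correlation coefficients" and concludes: "Given 30 subjects in each race group, we will be able to detect a difference of 0.3 with a one-sided alpha of 0.05". No power is given, and the two correlations appear only as symbols.

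Section a (Analyses) sets a general rule: "All statistical tests will be two-sided and will be performed using an alpha level of 0.05". On the association itself it says: "The correlation between change in pancreas lipid and change in first-phase C-peptide secretion will be examined, adjusting for insulin sensitivity". It mentions no comparison of that correlation between races. On race it says: "For Aim 3, the primary variable of interest is the race-by-diet interaction term", with separate analysis within each race if the interaction is significant.

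**The concern.** There are three linked problems.

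- **The claim is incomplete in a way that decides whether it is true.** The Fisher transformation stretches the scale as correlations approach 1. The same 0.3 gap is 0.310 on the z scale from 0 to 0.3, but 0.779 from 0.6 to 0.9. Without the correlations and the power, a detectable difference of 0.3 is not defined.
- **The alpha contradicts the plan's own rule.** A one-sided test is used here, while section a makes every test two-sided and declares no exception.
- **The comparison has no place in the analysis section.** A race-by-diet interaction asks whether the diet effect differs by race. It does not test whether two correlations differ, and neither does analysing each race separately.

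The plan's stated reason for 15 per diet-race group is the belief about race and the lipid association, and this is the only power statement for that belief. A reader who takes 0.3 at face value could read a non-significant between-race comparison as evidence of similar associations when the trial had little chance of showing a difference.

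**Working it through.** **Inputs.** From section b: 30 completers per race group, a difference of 0.3, one-sided alpha 0.05, Fisher z test. From section a: two-sided alpha 0.05 for all tests. Assumed: the weaker correlation (shown over a range) and 80% power, which the plan states only for the t-test. Correlations are taken as positive; the results are the same if both are negative.

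**Check of the t-test statement.** Noncentrality = (89.7 / 84.639) × sqrt(15/2) = 2.90 on 28 degrees of freedom. Two-sided 0.05 gives 80.0% power, so that figure reproduces.

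**The 0.3 figure.** It cannot be reproduced as written, because the power and the correlations are missing. The check is therefore what the named test delivers.

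SE = sqrt(1/27 + 1/27) = sqrt(2/27) = 0.2722, with 27 = 30 − 3.

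Power ≈ Φ(Δz / SE − z_α), where Δz = atanh(r + 0.3) − atanh(r), and z_α = 1.645 one-sided or 1.960 two-sided (the two-sided figures below also allow for the far tail, which adds 0.1 point or less).

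Example, 0.3 v 0.6: Δz = 0.384; 0.384 / 0.2722 = 1.41; Φ(1.41 − 1.645) = 41%.

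| Correlations | Δz | Power, one-sided | Power, two-sided |
|---|---|---|---|
| 0 v 0.3 | 0.310 | 30.6% | 20.6% |
| 0.3 v 0.6 | 0.384 | 40.7% | 29.1% |
| 0.5 v 0.8 | 0.549 | 64.6% | 52.3% |
| 0.55 v 0.85 | 0.638 | 75.8% | 64.9% |
| 0.6 v 0.9 | 0.779 | 88.8% | 81.7% |

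Simulation of bivariate normal data (100,000 replicates) agrees within about 1 point: 31.1%, 41.8%, 65.6% and 89.3% one-sided for weaker correlations of 0, 0.3, 0.5 and 0.6.

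**Where 0.3 reaches 80% power.** The z-scale difference needed is (1.645 + 0.842) × 0.2722 = 0.677 one-sided and 2.8016 × 0.2722 = 0.762 two-sided. A gap of 0.3 reaches these from 0.567 v 0.867 and from 0.595 v 0.895. With a gap of 0.3 and both correlations positive, the weaker one can lie between 0 and 0.7, so the one-sided claim fails over 0.567 / 0.7 = 81% of that range.

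**A check with no power benchmark.** An observed gap of 0.3 is just significant when Δz = z_α × 0.2722, which is 0.448 one-sided or 0.533 two-sided. The weaker observed correlation must then be at least 0.405 (one-sided) or 0.489 (two-sided).

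**Another reading of 0.3.** Taken as a difference on the z scale, 0.3 gives 29% power one-sided, so this does not rescue the claim.

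**What the design does detect, two-sided with 80% power.** The difference is tanh(atanh(r) + 2.8016 × SE) − r. If each correlation is adjusted for insulin sensitivity, one more degree of freedom is lost per group and SE = sqrt(2/26) = 0.2774.

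| Weaker correlation | Unadjusted | Adjusted |
|---|---|---|
| 0 | 0.64 | 0.65 |
| 0.3 | 0.49 | 0.50 |
| 0.5 | 0.36 | 0.37 |
| 0.6 | 0.30 | 0.30 |

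**The case against.** The best defence is that the sentence is under-specified rather than miscalculated. With power and correlations left out, 0.3 can be neither reproduced nor refuted, and it is true for some inputs. The plan sets no 80% benchmark for this comparison, and its reference to significance allows a looser meaning of detect. That much is fair, but even the looser meaning needs an observed weaker correlation of 0.41 or more, a condition the plan does not state. A claim made without qualification that fails over most of its range is wrong as written.

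The one-sided alpha can be explained by the directional belief about African-Americans stated just before it. This makes it understandable, but section a allows no exception.

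The 60 completers also have other support. Fifteen per diet-race group gives a 15 v 15 diet comparison within each race, which matches the t-test and the planned within-race analyses. This stands and limits the consequence. It does not supply power for the race belief that the plan itself gives as its reason.

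Finally, Supplementary Table 1 already reports week-12 data, so a restated figure cannot change recruitment. That is also true. What remains at stake is how a between-race comparison of correlations is tested and read.

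**Conclusion.** The concern holds. The statement omits the power and both correlations, and the design does not deliver a detectable difference of 0.3 unless both correlations are strong: about 0.57 v 0.87 one-sided, or 0.60 v 0.90 under the plan's two-sided rule. For weaker correlations from 0 to 0.5, two-sided power for a true difference of 0.3 is only 21% to 52%. The one-sided alpha contradicts section a, and the comparison is missing from the listed analyses.

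The thresholds rest on an assumed 80% power, and the power figures on assumed starting correlations. Adjusting the between-race test for insulin sensitivity is also an assumption, since the plan states it only for the overall correlation; it moves the detectable difference by at most about 0.01. This should be fixed, but the primary outcomes, the t-test power and the Aim 3 interaction test are unaffected.

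**What to change.** Issue a dated clarification that leaves the existing protocol sentence on record and restates the figure, for example:

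> With 30 per race group, two-sided alpha 0.05 and 80% power, the Fisher z test (SE = sqrt(2/27)) detects a difference in correlations of about 0.64, 0.49, 0.36 or 0.30 if the weaker correlation is 0, 0.3, 0.5 or 0.6 (assumed values). Adjusting each correlation for insulin sensitivity (SE = sqrt(2/26)) gives about 0.65, 0.50, 0.37 and 0.30.

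In section a, list the between-race comparison of correlations as exploratory and two-sided, and say whether it is adjusted for insulin sensitivity. Note that it was listed after week-12 results were available (Supplementary Table 1), and that a non-significant result is not evidence of similar associations.

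The cost is text only. The stated detectable difference becomes less favourable unless both correlations are strong. No extra patients are needed, and the sample size, primary outcomes and Aim 3 test stay as they are.

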Given that patients were removed from medication prior to study initiation, and were carefully monitored for glycemic control during the study, it is important to ensure that they make a smooth transition to a free-living situation. Following final testing, all study participants will be given access to continued diet/nutrition support, provided by the study team, to assure a smooth transition to a free-living diet. Patients will be able to choose their preferred diet (they may choose to stay on their assigned intervention diet, or to transition to a different diet).

Medical management, including of medication type and dosage, will be available during this transition. All patients will demonstrate stable glycemic control on a given diet and medication regimen before exiting the study.

[figure not shown]
Supplementary Table 1. Insulin sensitivity from the hyperglycemic clamp and OGTT (Matsuda Index) by race and diet.

Insulin sensitivity measure	Baseline Mean (SD)	Week 12 Mean (SD)	Change Mean (SEM)	P for change
Hyperglycemic clamp				
EA HC	9.13 (7.42)	15.87 (16.65)	5.31 (4.17)	0.24
EA CR	6.33 (5.74)	9.03 (6.06)	2.3 (2.74)	0.42
AA HC	6.65 (4.49)	8.12 (4.77)	1.28 (0.72)	0.09
AA CR	10.24 (8.99)	12.16 (19.96)	4.07 (3.42)	0.26
Matsuda Index (OGTT)				
EA HC	2.46 (1.91)	3.36 (2.27)	0.89 (0.49)	0.1
EA CR	2.08 (1.02)	2.74 (1.35)	0.66 (1)	0.083
AA HC	2.18 (1.16)	5.99 (2.98)	0.66 (0.32)	0.06
AA CR	3.11 (3.99)	4.39 (2.94)	1.28 (0.75)	0.11

Abbreviations: EA: European American, AA: African American, CR: Carbohydrate restricted diet, HC: Higher carbohydrate diet.

Supplementary Fig. 1. Schematic of the hyperglycemic clamp. Glucose is injected as a bolus over 2 minutes at 0 and 150 minutes. Arginine is infused from 180-185 minutes. After the time 0 bolus, blood glucose is brought to 50 mg/dL above basal and held there until minute 30 using an infusion of 20% dextrose. After the time 150 bolus, blood glucose is brought to 300 mg/dL and held there until minute 180 using an infusion of 20% dextrose. Data from a representative participant are shown at baseline (open circles) and 12 weeks (filled squares).

Supplementary Fig 2. CONSORT diagram.

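### Supplementary Table 1 gives insulin-sensitivity change only as within-cell P values by race and diet; it omits the planned mixed-model time and time-by-diet estimates, so it cannot answer the randomised question or show absence of change.

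*Combined protocol and SAP*

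**What the plan says.** The Statistics section, part a (Analyses), sets the method: "The primary analysis for each aim will be a mixed model, using all available data and utilizing the estimated correlation between measurement times". For Aim 2, "Statistical models will include time, diet, and the time-by-diet interaction", and the plan extends this to insulin sensitivity: "Similar analyses will be conducted for PhiD from the MMTT, and insulin sensitivity from the hyperglycemic clamp". The Matsuda index is not named there.

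Race enters under Aim 3 as a race-by-diet term added to the models of Aims 1 and 2. A split by race is conditional: "If either of these interaction terms is significant, the data will be analyzed separately within each race group". For all analyses, "variables known to deviate from a normal distribution will be log transformed". On testing, "All statistical tests will be two-sided and will be performed using an alpha level of 0.05".

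The table headed "Supplementary Table 1. Insulin sensitivity from the hyperglycemic clamp and OGTT (Matsuda Index) by race and diet" has four rows per measure (EA HC, EA CR, AA HC, AA CR). Each row has a baseline mean, week 12 mean, change with SEM, and a P value for change. It prints no n, overall time effect, between-diet difference or interaction test, and it does not name the test behind its P values.

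**The concern.** The trial randomised diet, so the question for any outcome is whether change differs between CR and HC. A P value for change inside one cell does not address that. Four such values side by side invite a comparison of significance levels that is not a test of anything.

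Splitting also costs precision. All eight P values lie between 0.06 and 0.42, and a reader could take the table to show that insulin sensitivity did not move. This matters because insulin sensitivity is a candidate covariate in the Aim 2 models, whose primary outcome is first-phase C-peptide, and is the adjustment variable for the planned correlation between change in pancreas lipid and change in first-phase C-peptide. Whether it changed, and whether it changed differently by diet, bears on how both results are read.

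Finally, the plan makes race-specific analysis conditional on a significant interaction, and the documents show none.

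**Working it through.** **Inputs.** Clamp change (SEM) and P from Supplementary Table 1: EA HC 5.31 (4.17), 0.24; EA CR 2.3 (2.74), 0.42; AA HC 1.28 (0.72), 0.09; AA CR 4.07 (3.42), 0.26. Cell sizes are not printed. I assume 9 to 17 per cell; the plan's target is 15 with complete data.

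**1. What the printed P values are.** Take t = change/SEM on n - 1 df.

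- Clamp t values are 1.27, 0.84, 1.78 and 1.19. With 2.3 read as 2.30, the printed P values fit n of 8-10, 9-17, 15 or more, and 10-15 in turn.
- Three of the four Matsuda rows also fit, so seven of eight are consistent with a paired t-test inside the single cell.
- The exception is Matsuda EA CR: 0.66/1 = 0.66 gives P about 0.52, not 0.083. An SEM near 0.35 would be needed.

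**2. Change against the column means (clamp).**

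| Cell | Week 12 minus baseline | Printed change |
|---|---|---|
| EA HC | 15.87 - 9.13 = 6.74 | 5.31 |
| EA CR | 9.03 - 6.33 = 2.70 | 2.3 |
| AA HC | 8.12 - 6.65 = 1.47 | 1.28 |
| AA CR | 12.16 - 10.24 = 1.92 | 4.07 |

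None agrees. Changes computed on complete pairs, beside means on everyone measured, would explain this, but the table does not say so. Matsuda AA HC is harder to explain: 5.99 - 2.18 = 3.81 against a printed change of 0.66.

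**3. Diet contrast in clamp change (CR minus HC).**

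- EA: 2.30 - 5.31 = -3.01, SE = sqrt(2.74² + 4.17²) = 4.99.
- AA: 4.07 - 1.28 = 2.79, SE = sqrt(3.42² + 0.72²) = 3.49.
- Average: (-3.01 + 2.79)/2 = -0.11, SE = sqrt(4.99² + 3.49²)/2 = 3.05.
- 95% CI about -6.4 to 6.2 at 9 per cell (Satterthwaite df about 22). The half-width of 6.3 is about 78% of the mean baseline, (9.13 + 6.33 + 6.65 + 10.24)/4 = 8.09.
- From the column means in step 2 the same contrast is (2.70 + 1.92)/2 - (6.74 + 1.47)/2 = -1.80. The estimate therefore depends on which participants are counted, which is what an analysis of all available data should settle.

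**4. Race-by-diet difference in clamp change.** 2.79 - (-3.01) = 5.80, SE = sqrt(4.99² + 3.49²) = 6.09, t = 0.95, P about 0.35. These figures give no support for splitting by race.

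**5. Overall clamp change, as an approximation only.**

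- Equal weights: (5.31 + 2.30 + 1.28 + 4.07)/4 = 3.24. SE = sqrt(17.39 + 7.51 + 0.52 + 11.70)/4 = 1.52. t = 2.13. Satterthwaite df is 22 to 44 for 9 to 17 per cell, so P = 0.045 to 0.039. The rise is 3.24/8.09, about 40% of baseline.
- Inverse-variance weights: +1.56, SE 0.67, about 19% of baseline, P about 0.03 to 0.04. AA HC carries about 87% of the weight.
- Equal weights, leaving out one cell, over the same range of n: without EA HC, P 0.095-0.104; without EA CR, 0.059-0.068; without AA HC, 0.060-0.067; without AA CR, 0.088-0.099.

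**6. Scale.** Two week 12 clamp SDs exceed their means (16.65 against 15.87; 19.96 against 12.16). This suggests skewness, so the log rule may apply. No log-scale result can be derived from the table.

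**The case against.** The documents contain a methods text and one supplementary table, with no results section. A descriptive table by cell does not show that the mixed model was not run or is not reported elsewhere. A reader might infer that cell-wise tests replaced the planned analysis; the documents support only that this table does not report it. That part of the objection stands.

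A reader might also infer that the authors claim unchanged insulin sensitivity, or C-peptide recovery independent of it. No sentence says so, and the plan adjusts for insulin sensitivity. What can be criticised is the reading that the table invites.

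The most tempting reading is that the table conceals a significant overall rise. The clamp average does fall below 0.05 under both weightings, but it cannot stand in for the planned model. It uses a change column that looks complete-case, cell sizes that are assumed, and the raw scale. Its size halves with the weighting, and leaving out any one cell takes the equal-weight P above 0.05. The Matsuda rows cannot shore it up: two of four contradict themselves, and the plan does not name that index for this model.

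Nor would an overall rise answer the randomised question, since it is a before-after change common to both diets. The reporting gap remains after all this: neither the diet contrast nor its imprecision can be seen in the table.

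**Conclusion.** The point holds as a reporting and interpretation defect, with moderate confidence. The table does not carry the time and time-by-diet estimates planned for clamp insulin sensitivity, and it splits by race without showing the interaction that the plan requires first (implied difference 5.80, SE 6.09, P about 0.35). Its P values cannot support a statement about diet, because the implied contrast of -0.11 is compatible with differences of about 6 units either way. Nor can they support a statement of no change.

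The pooled clamp rise of +3.24 should be treated only as a warning against reading the table as null. All clamp figures here assume independent cells, correct printed SEMs and 9 to 17 participants per cell. The Matsuda rows give no usable support until EA CR and AA HC are reconciled.

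**What to change.** - Report, from the planned mixed model on all available data, the time effect, the CR-minus-HC difference in change, and the race-by-diet difference in change, each with a 95% CI. Log-transform if the plan's rule applies, and say which scale was used. If these estimates appear elsewhere, cite the place in the table.
- Print n per cell at baseline, at week 12 and for the change.
- Keep the cell means as description and drop the P-value column.
- Correct or explain Matsuda EA CR (SEM against P), Matsuda AA HC (change against means) and the clamp changes that differ from their column means.
- Say whether the Matsuda index is analysed by the same model, since the plan names only the clamp measure.
- Do not infer unchanged insulin sensitivity from cell-wise P values, and describe any overall rise as an uncontrolled time effect.

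The cost is one re-run of a planned model, a check of a few entries and a new table layout.
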